5.3 Randomization or Treatment Allocation

Randomization will occur centrally using an interactive voice response system / integrated web response system (IVRS/IWRS). There are 2 randomized treatment arms. Subjects will be assigned randomly in a 2:1 ratio to IMI/REL + placebo to CMS (Treatment Group 1; N=~36) or CMS + IMI (Treatment Group 2; N=~18), respectively. Subjects enrolled into the open-label arm (Treatment Group 3) will be provided with IMI/REL through IVRS/IWRS as well.

5.4 Stratification

Randomization will be stratified according to the following infection types:

1. HABP/VABP
2. cIAI
3. cUTI

Subjects diagnosed with more than one of the infection types listed above can be enrolled into the study as long one of the infections listed above is identified as the primary site. Both the primary site of infection as well as any secondary infection sites will be documented on the relevant eCRF(s). Stratification will be determined based on a hierarchy of the 3 specified infection types. Specifically, subjects with multiple sites of infection, regardless of the primary site, will be stratified in order of priority (based on the presence of any of the 3 infection types) into the HABP/VABP stratum first, followed by the cIAI stratum, and finally the cUTI stratum.

Given the potential differences in severity of the various infection types, enrollment of an excess number of subjects in a stratum with less severe disease could have significant impact on the ability to evaluate the efficacy endpoints. For this reason, randomization will be stratified by infection type. Approximately 18 subjects will be enrolled into each of the 3 strata. Once 18 subjects have been enrolled into an individual stratum, this stratum may be considered fully enrolled but enrollment into that stratum may remain open at the discretion of the Sponsor until the other strata have reached full capacity. Hierarchical stratification of

subjects with multiple infection sites will continue regardless of status of enrollment in each stratum.

A total of 15 mMITT subjects are required per infection site (45 total across the 3 strata). At the discretion of the Sponsor, enrollment may be stopped prior to reaching 54 total subjects if a sufficient number of mMITT subjects have been obtained. Enrollment may also be extended beyond 54 subjects at the discretion of the Sponsor for the following reasons: 1) if additional subjects beyond 54 are required to obtain the target number of mMITT subjects; or 2) if enrollment in any individual stratum has not been completed, while other strata remain open (even after a sufficient number of mMITT subjects have been obtained in those strata), until all 3 strata have reached full capacity (i.e., 15 mMITT evaluable subjects each).

The primary site of infection as well as any secondary infection sites will be documented on the relevant eCRF(s) for subjects enrolled into Treatment Group 3 as well. Since Treatment Group 3 will not be randomized, stratification variables will not be used for this group and no limits will be placed on the number of subjects per infection site. Enrollment in Treatment Group 3 will be ongoing until enrollment is completed in the randomized cohort.

5.5 Concomitant Medications/Vaccinations (allowed & prohibited)

Medications or vaccinations specifically prohibited in the exclusion criteria are not allowed during the ongoing trial. Listed below are some specific restrictions for concomitant therapy or vaccination during the course of the trial. If there is a clinical indication for one of these or other medications or vaccinations specifically prohibited during the trial, discontinuation from trial therapy or vaccination may be required. The investigator should discuss any questions regarding this with the Sponsor Clinical Director. The final decision on any supportive therapy or vaccination rests with the investigator and/or the subject's primary physician. However, the decision to continue the subject on trial therapy or vaccination schedule requires the mutual agreement of the investigator, the Sponsor and the subject.

NOTE: With the exception of >24 hours of colistin for subjects in Treatment Groups 1 and 2 (see Section 5.1.3.1, Criterion #4) there are no restrictions to prior antimicrobial therapy.

The following concomitant medications/therapies are NOT permitted in this study:

1. Valproic acid/divalproex sodium
2. Non-study IV, oral, or inhaled antibacterial treatments with known coverage of Gram-negative bacteria of interest (i.e., Enterobacteriaceae, *Pseudomonas* spp. and Gram-negative anaerobic bacilli).

Importantly, the following antibacterial medications are permitted:

- a. IV vancomycin, IV daptomycin, or IV linezolid to treat confirmed or suspected MRSA infection. If added, IV vancomycin, daptomycin, or linezolid should be used according to the investigator's usual practice. Daptomycin is not indicated for the treatment of HABP/VABP.

- b. IV linezolid or IV daptomycin to treat confirmed or suspected VRE infection. If added, linezolid or daptomycin should be used according to the investigator's usual practice. Daptomycin should not be used to treat HABP/VABP.
 - c. TMP/SMX or other standard-of-care agent for prophylaxis of opportunistic infection (e.g., *P. jiroveci* infection) in immunocompromised subjects.
3. Use of systemic antifungal therapy for disseminated fungal infection, fungemia, or for pulmonary infection in HABP/VABP subjects.

Antifungal medications are permitted in the following clinical situations:

- a. Antifungal medications for treatment of mucocutaneous infection (e.g., vaginal candidiasis, onychomycosis).
- b. Antifungal medications for prophylaxis of invasive fungal infections, such as in immunocompromised patients.
- c. Antifungal medications for treatment of fungal pathogens isolated in polymicrobial cIAI, if treatment of isolated fungal pathogens is required.

5.6 Rescue Medications & Supportive Care

No rescue or supportive medications are specified to be used in this trial.

5.7 Diet/Activity/Other Considerations

There are no dietary or activity restrictions in this study, except as medically indicated.

5.8 Subject Withdrawal/Discontinuation Criteria

Subjects may withdraw consent at any time for any reason or be dropped from the trial at the discretion of the investigator should any untoward effect occur. In addition, a subject may be withdrawn by the investigator or the Sponsor if enrollment into the trial is inappropriate, the trial plan is violated, or for administrative and/or other safety reasons. Specific details regarding discontinuation or withdrawal procedures; including specific details regarding withdrawal from Future Biomedical Research, are provided in Section 7.1.4 – Other Procedures.

In this trial, a subject may discontinue from IV study therapy but continue to participate in the regularly scheduled activities, as long as the subject does not withdraw consent. Discontinuation from IV study therapy is permanent. Once a subject has discontinued IV study therapy, even though he/she continues to be monitored in the trial, he/she shall not be allowed to begin IV study therapy again.

A subject must be discontinued from the trial for any of the following reasons:

- 1. The subject or legal representative (such as a parent or legal guardian) withdraws consent.

2. The subject has a medical condition or personal circumstance which, in the opinion of the investigator and/or Sponsor, places the subject at unnecessary risk through continued participation in the trial or does not allow the subject to adhere to the requirements of the protocol.

A subject must be discontinued from IV study therapy (but should continue to be monitored in the trial) for any of the following reasons:

1. Any of the following post-baseline elevations in liver transaminase levels:

In subjects without baseline transaminase elevations:

- ALT or AST ≥ 8 X ULN
- ALT or AST ≥ 3 X ULN accompanied by total bilirubin > 2 X ULN **OR** INR > 1.5
- ALT or AST ≥ 3 X ULN with the appearance of fatigue, nausea, vomiting, right upper quadrant pain or tenderness, fever (defined as body temperature $\geq 38.0^{\circ}\text{C}$ [$\geq 100.4^{\circ}\text{F}$]), rash, and/or eosinophilia ($> 5\%$)

NOTE: In subjects in whom fatigue, nausea, vomiting, and right upper quadrant pain or tenderness was a part of the subject's presenting illness, the subject may continue on therapy if there is no elevation in transaminases from baseline measurements. In such subjects who experience a return of their original symptoms with accompanying elevations in transaminases it may be difficult to determine the cause, and investigators may discuss subjects in this situation with the Sponsor Clinical Director prior to discontinuation, if desired.

In subjects with preexisting transaminase elevations,

- Further increase in transaminases to ≥ 8 X ULN [with at least 50% increase from transaminase values collected at randomization (Day 1)] that is not anticipated from their underlying medical condition.
- ALT or AST ≥ 3 X ULN and new onset of clinical signs and symptoms of fatigue, nausea, vomiting, right upper quadrant pain or tenderness, fever (defined as body temperature $\geq 38.0^{\circ}\text{C}$ [$\geq 100.4^{\circ}\text{F}$]), rash, and/or eosinophilia ($> 5\%$)
- Clinically significant worsening of liver function associated with further transaminase elevations in a subject with abnormal transaminase levels already meeting the above criteria (i.e., ≥ 8 X ULN; ALT or AST ≥ 3 X ULN and new onset of clinical signs and symptoms listed) at baseline.

The subject will discontinue from study therapy, but will continue to participate in the study and will be assessed according to all study planned study procedures through the final study visit and will be evaluated for blood chemistry and hematology (including, at minimum, ALT, AST, alkaline phosphatase, bilirubin (direct + indirect) and creatine phosphokinase) until values return to within normal range. The trial site guidance for assessment and follow up of liver function test (LFT) elevations can be found in the Investigator Trial File Binder.

2. A post-baseline decline in estimated or actual creatinine clearance to a value of less than 15 mL/min.
3. The subject requires initiation of hemodialysis or peritoneal dialysis.
4. The subject has a confirmed positive serum or urine (sensitivity of < 25 million IU/L is required if using urine test) pregnancy test.
5. A physician investigator feels it is in best interest of the subject to discontinue for any reason, including, but not limited to, the need for alternative non-study antibacterial therapy.
6. A new imipenem-resistant Gram-negative bacterium is isolated from an infection site during study therapy and is not susceptible to IMI/REL and colistin.

NOTE: Since subjects enrolled into Treatment Group 3 are required to have a colistin-resistant infection at randomization, development of a new colistin-resistant infection would not require discontinuation.

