7.1.4 Other Procedures

7.1.4.1 Withdrawal/Discontinuation

Subjects who discontinue/withdraw from IV study therapy prior to completion of the IV study therapy regimen should continue to be followed for all remaining study visits.

When a subject discontinues/withdraws from participation in the trial, all applicable activities scheduled for the final trial visit should be performed at the time of discontinuation. Any adverse events which are present at the time of discontinuation/withdrawal should be followed in accordance with the safety requirements outlined in Section 7.2 - Assessing and

Recording Adverse Events. Please refer to Section 5.8 for trial-specific subject discontinuation criteria.

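### Section 5.8 permits, and under one item requires, removal from the whole trial without withdrawn consent, and the plan gives no route to Day 28 survival status for those subjects

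*Combined protocol and SAP*

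**What the plan says.** Section 5.8 describes two kinds of exit.

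**Leaving the trial**
- The investigator has discretion to let a subject "be dropped from the trial at the discretion of the investigator should any untoward effect occur". No severity threshold is attached.
- The next sentence covers the investigator and the Sponsor: "a subject may be withdrawn by the investigator or the Sponsor if enrollment into the trial is inappropriate, the trial plan is violated". Its closing grounds are administrative and other safety reasons.
- Trial discontinuation is mandatory for two reasons. One is withdrawn consent. The other is a medical condition or personal circumstance that, in the opinion of the investigator and/or Sponsor, "places the subject at unnecessary risk through continued participation in the trial" or prevents adherence.

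**Stopping IV therapy only**
- Section 5.8 says "a subject may discontinue from IV study therapy but continue to participate in the regularly scheduled activities", provided consent is not withdrawn.
- A separate list opens "A subject must be discontinued from IV study therapy (but should continue to be monitored in the trial". It covers specified liver elevations, creatinine clearance below 15 mL/min, dialysis, pregnancy, certain new resistant isolates, and a physician investigator's best-interest judgment on any ground.

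Section 7.1.4.1 attaches different follow-up to each kind. Subjects who stop therapy "should continue to be followed for all remaining study visits". For subjects who leave the trial, "all applicable activities scheduled for the final trial visit should be performed at the time of discontinuation", and adverse events present on that day continue to be followed. Section 7.1.3.5.3 calls for Day 28 survival status in each subject, without saying how it is obtained after a trial exit.

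**The concern.** The distinction between stopping treatment and ending observation is sound, but the grounds for the two overlap. An untoward effect, a safety worry or a judgment about the subject's interest can lead down either route, and nothing says which comes first. One route keeps the later creatinine draws, the EFU visit and the Day 28 visit. The other replaces them with a single assessment on the day of exit.

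Two things are at stake.
- **Day 28 and EFU endpoints.** A subject removed early is missing for the primary endpoint and counts as a failure, although survival at Day 28 (HABP/VABP) might have been established by a simple contact.
- **Nephrotoxicity.** Events that arise after exit may not be seen, because scheduled laboratory tests have ended.

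If removals follow toxicity they could differ by arm, since Section 4.2.3.2 singles out renal toxicity as the concern with colistin.

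**Working it through.** **1. The two routes side by side**

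| Situation | Route in Section 5.8 | Scheduled visits afterwards |
|---|---|---|
| Listed liver elevation, creatinine clearance <15 mL/min, dialysis | Stop therapy | Kept |
| Physician's best-interest judgment (therapy item 5) | Stop therapy | Kept |
| Opinion of unnecessary risk or inability to adhere (trial item 2) | Leave trial, mandatory | Ended |
| Any untoward effect (investigator) | Leave trial, discretionary | Ended |
| Plan violation, inappropriate enrollment, administrative or other safety reason (investigator or Sponsor) | Leave trial, discretionary | Ended |

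Rows 2 and 3 send closely similar judgments to opposite outcomes.

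**2. Does the keep-monitoring list cover the nephrotoxicity endpoint?** Only in part. Table 9 counts, for a normal baseline, a doubling of creatinine or a creatinine clearance fall of at least 50%. With pre-existing dysfunction it counts a creatinine rise of at least 1 mg/dL, a clearance fall of at least 20%, or renal replacement therapy. As an illustration, with baseline creatinine in the normal category, a clearance fall from 100 to 50 mL/min is (100 − 50)/100 = 50%. That is an endpoint event, yet it is far above the 15 mL/min trigger. Only the best-interest item could keep such a subject in follow-up, and it competes with the discretionary drop.

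**3. How a dropped subject enters the analysis.** Table 16 sets Missing = Failure for overall response, Day 28 clinical response and Day 28 mortality, and uses observed data for nephrotoxicity. Section 5.9 rules out replacement. The mMITT definition (Section 8.2.4.1) depends on dosing and baseline pathogen, so a dropped subject stays in the denominator.

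**4. Size per subject.** Section 8.2.7 plans on 15 (Group 2) and 30 (Group 1), with 5 and 10 per infection type. One otherwise favorable subject counted as a failure costs 1/N:
- 1/15 = 6.7 points and 1/30 = 3.3 points overall;
- 1/5 = 20 points and 1/10 = 10 points within one infection type.

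**5. Effect on the planned intervals.** The Agresti–Coull interval is p̃ ± z√(p̃(1 − p̃)/ñ), with ñ = n + z², p̃ = (x + z²/2)/ñ and z = 1.96. For 9/15, ñ = 18.84 and p̃ = 10.92/18.84 = 0.580, which gives (35.7, 80.2). For 21/30 it gives (52.0, 83.5). Both match Table 18. The number dropped below is an assumption.

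| Dropped in that group | Group 2, from 9/15 | Group 1, from 21/30 |
|---|---|---|
| 0 | 60.0% (35.7, 80.2) | 70.0% (52.0, 83.5) |
| 1 | 53.3% (30.1, 75.2) | 66.7% (48.7, 80.9) |
| 2 | 46.7% (24.8, 69.9) | 63.3% (45.5, 78.2) |
| 3 | 40.0% (19.8, 64.3) | 60.0% (42.3, 75.4) |

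Starting from a difference of 70.0 − 60.0 = 10.0 points, one drop in Group 2 alone gives 70.0 − 53.3 = 16.7. One drop in Group 1 alone gives 66.7 − 60.0 = 6.7.

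**6. Mortality.** If failure is read as death for this endpoint, a true 3/15 = 20.0% becomes 4/15 = 26.7% with one dropped survivor and 5/15 = 33.3% with two.

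**7. Nephrotoxicity.** Section 8.2.4.2 needs only a baseline and one post-dose creatinine, so a subject who leaves before meeting Table 9 can be counted as event-free. Fisher's exact test gives p = 0.036 for 1/30 vs 4/15 and p = 0.101 for 1/30 vs 3/15. Both agree with Table 19. One unseen Group 2 event would move the result from the first to the second.

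**The case against.** The strongest reply is that the protocol already protects most of the subjects who matter, and much of that reply stands.

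- **Toxicity.** A reader might infer that follow-up ends precisely in the subjects with toxicity. The text does not support that. The specified liver and severe renal toxicities, and a physician's best-interest stop on any ground, all lead to continued monitoring. Removals for plan violation or administrative reasons need not involve toxicity at all.
- **Discretion.** The untoward-effect ground permits removal but does not require it, and it belongs to the investigator alone. The Sponsor's discretionary grounds are those in the following sentence ("the trial plan is violated, or for administrative and/or other safety reasons", plus inappropriate enrollment).
- **Safety follow-up.** It is shortened, not abolished. Adverse events present at exit are followed. On-therapy laboratory abnormalities judged to be adverse events are followed until resolved or stable (Section 6.0 footnotes), with repeat testing under Section 7.1.3.1. The reporting window of 14 days after treatment in Section 7.2 states no exception for withdrawn subjects. Reversibility of a known kidney injury should therefore still be documented.
- **Nephrotoxicity.** A subject removed because of an injury that already meets Table 9 is counted as an event. Only later events are at risk.
- **Frequency.** A reader might multiply the top of the 0 to 30% colistin nephrotoxicity range in Section 4.1.3 by 18 subjects (0.30 × 18 = 5.4) and expect about five withdrawals. That range is an incidence of toxicity, described there as mostly mild and reversible. It is not a rate of leaving the trial.

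What the reply leaves open is the set of subjects removed under the discretionary sentences or trial item 2. For them no scheduled visit or laboratory test remains, and Section 7.1.3.5.3 states a requirement without a means of meeting it.

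**Conclusion.** The point holds as a conflict between provisions with a limited but real effect on missing data. Sections 5.8 and 7.1.4.1 can end scheduled follow-up for reasons other than withdrawn consent, while neighboring text keeps subjects with similar problems under observation and Section 7.1.3.5.3 expects Day 28 status for everyone.

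The size is 6.7 points per otherwise favorable subject lost in the CMS + IMI group and 3.3 points in the IMI/REL group. This rests on the planned 15 and 30 mMITT subjects, exit before the endpoint is assessed, and Missing = Failure. The total effect cannot be stated because no drop rate is given, and none of the figures above is a forecast. A difference between arms is possible if removals follow toxicity, but the documents do not establish one. The mortality figures also assume that failure means death. This should be corrected; it does not undermine the design.

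**What to change.** Reconcile Section 5.8 with Sections 7.1.4.1 and 7.1.3.5.3 by adding two statements:

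1. Unless consent is withdrawn, a subject withdrawn for any other reason stays in the scheduled visits, safety laboratory tests, adverse event collection and Day 28 survival assessment, as far as feasible.
2. For subjects who stop attending visits, a Day 28 vital-status contact is sought with their agreement.

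Leave the rules on stopping IV therapy as they are. In particular, do not move the discretionary grounds into the list of mandatory reasons for stopping therapy. That would change treatment, and this point concerns only observation.

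The cost is a wording amendment and minor site effort to follow subjects who are off therapy. The visits are already in the trial flow chart.

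### Section 5.8 gives subjects who enter with raised ALT or AST no stopping threshold for the combined transaminase and bilirubin (or INR) pattern that stops everyone else

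*Combined protocol and SAP*

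**What the plan says.** Section 5.8 requires IV study therapy to stop, with follow-up continuing, for a set of liver findings introduced as "Any of the following post-baseline elevations in liver transaminase levels". Two lists follow.

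The first is headed "In subjects without baseline transaminase elevations". It has three limbs:
- ALT or AST at 8x ULN or more.
- ALT or AST at 3x ULN or more, "accompanied by total bilirubin" above 2x ULN or INR above 1.5.
- ALT or AST at 3x ULN or more with the appearance of listed signs or symptoms.

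The second is headed "In subjects with preexisting transaminase elevations". It also has three limbs, but not the same three:
- A further increase to 8x ULN or more that is at least 50% above the Day 1 value and "that is not anticipated from their underlying medical condition".
- ALT or AST at 3x ULN or more and "new onset of clinical signs and symptoms of fatigue, nausea, vomiting, right upper quadrant pain or tenderness, fever", rash or eosinophilia.
- "Clinically significant worsening of liver function associated with further transaminase elevations in a subject with abnormal transaminase levels already meeting the above criteria", where those criteria are 8x ULN, or 3x ULN with the listed signs, at baseline.

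The same section makes any stop permanent. Its reason 5 requires a stop when a physician investigator judges this best for the subject. Section 7.2.3.2 makes two liver patterns events of clinical interest (ECIs), reportable within 24 hours. ECI 2 is ALT or AST at 3x ULN or more with bilirubin at 2x or more and alkaline phosphatase below 2x. ECI 3 is a confirmed ALT or AST at 5x ULN or more.

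**The concern.** The limb that joins a transaminase rise to a rise in bilirubin or INR appears only in the first list. It asks whether liver function is failing, not only whether enzymes have leaked. Subjects who start with abnormal enzymes have no numeric stop for that pattern unless ALT or AST reaches at least 8x ULN or a listed sign appears. Jaundice, bilirubin and INR are not among the listed signs.

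The plan treats the pattern as important: with alkaline phosphatase below 2x ULN, it is a Tier 1 safety event in section 8.2.3.2. Affected subjects can enrol. Neither exclusion list (5.1.3.1, 5.1.3.2) has a transaminase limit, although both let the investigator exclude for a laboratory abnormality. Appendix 12.5 accepts liver abscess and perforated cholecystitis as qualifying intra-abdominal infections. What is at stake is patient safety in a small group, not the efficacy estimates.

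**Working it through.** The plan states no figure to reproduce here. The check applies each limb literally to the same on-treatment values. All thresholds come from section 5.8.

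**On-treatment values used:** ALT 7.9x ULN, bilirubin 4x ULN, no new listed sign or symptom.

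**Subject A, normal Day 1 ALT (first list).**
- 8x limb: 7.9 < 8, not met.
- Combined limb: 7.9 ≥ 3 and 4 > 2, met.
- Result: mandatory stop.

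**Subject B, Day 1 ALT 2x ULN (second list).**
- Limb 1 needs both 8x ULN and 1.5 × Day 1, so the trigger is max(8, 1.5 × 2) = max(8, 3) = 8x ULN. 7.9 < 8, not met, although ALT has risen 7.9/2.0 = 3.95-fold.
- Limb 2: 7.9 ≥ 3, but there is no new listed sign. Not met.
- Limb 3 needs a baseline of 8x, or of 3x with listed signs. Baseline is 2x, not met.
- Result: no threshold-based liver stop.

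**Subject C, Day 1 ALT 6x ULN without listed signs (second list).**
- Limb 1 trigger is max(8, 1.5 × 6) = 9x ULN. 7.9 < 9, not met.
- Limbs 2 and 3 fail for the same kind of reason.
- Result: no threshold-based liver stop. Once Day 1 exceeds 8/1.5 = 5.33x ULN, the limb 1 trigger is above 8x.

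**Size of the shift.** With bilirubin above 2x ULN and no listed sign, the ALT/AST trigger is 3x in the first list and at least 8x in the second: 8/3 = 2.67 times as high.

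**Do other provisions supply the missing threshold?**

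| Provision | Applies to subject B? | Sets a stop? |
|---|---|---|
| ECI 2 (7.2.3.2) | Yes, if alkaline phosphatase is below 2x ULN and the rise is not anticipated | No, reporting only; INR not used |
| ECI 3 (7.2.3.2) | Yes, if confirmed on repeat and not anticipated | No, reporting only |
| Reason 5 (5.8) | Yes, if the investigator judges so | Yes, but with no threshold |
| Investigator Trial File Binder | Not in the documents | Described as assessment and follow-up guidance |

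**Data needed for the missing limb.** ALT, AST and total bilirubin are in Table 14 and are scheduled for Day 1, Day 3 and every 3 days to end of therapy. INR is not in Table 14, so only a local result would exist.

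**The case against.** The strongest reply is that the omission is a defensible clinical choice. Sepsis and biliary disease can themselves raise bilirubin and INR, a stop is permanent, and section 4.2.1 stresses how few alternatives these patients have. Section 4.1.1 describes a PN004 subject on relebactam 250 mg who met ECI 2, normalised on continued therapy and was considered a cure. Reason 5 stands in the same list of mandatory stops, and subject B would be reported under ECI 3 once the value was confirmed. Much of this stands. It does not supply a threshold, and nothing in the documents says that the limb was left out on purpose. The plan already handles anticipated rises by a qualifier in limb 1, and the same device would serve here.

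The documents do not support several stronger readings that a reader might draw:
- **Such subjects would go unnoticed or simply be kept on drug.** ECI reporting and reason 5 argue against this.
- **The symptom limb stops subjects whose enzymes have not risen.** The lead-in limits the whole rule to post-baseline elevations.
- **The Phase II ECI 2 count gives the frequency.** ECI 2 excludes alkaline phosphatase at 2x ULN or more and ignores INR, and the share of subjects with preexisting elevations is not given.
- **Relebactam has a known serious liver signal.** Section 4.1.1 calls the Phase I rises generally mild; in PN001 they were reversible and also seen with imipenem alone. It reports no evidence of significant hepatotoxicity in Phase II.
- **No one can tell who counts as preexisting.** The paired headings and the Day 1 reference in limb 1 point to a value above ULN on Day 1, though no cut-off is written.

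**Conclusion.** The gap is real and specific. Subjects with raised Day 1 ALT or AST who rise to between 3x and below 8x ULN, with bilirubin above 2x ULN (or INR above 1.5) and no new listed sign, meet no threshold-based liver stop; subjects with normal Day 1 values and the same results must stop. The exception is the severely abnormal baseline group covered by limb 3. What is missing is a numeric rule, not all protection.

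The conclusion assumes that preexisting means above ULN on Day 1. If it meant 3x ULN or more, subjects entering between 1x and 3x would fall under the first list and only those entering at 3x or above would be affected. The expected number of subjects is small and cannot be estimated from the documents. No effect on the efficacy estimates is claimed. This is an inexpensive safety improvement worth making.

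**What to change.** In section 5.8, add one limb to the list for preexisting elevations: *ALT or AST at least 3x ULN and higher than on Day 1, together with total bilirubin above 2x ULN or (where measured) INR above 1.5, that bilirubin or INR also being higher than on Day 1, and not expected from the underlying medical condition or from anticoagulation.* State that the list applies to subjects whose Day 1 ALT or AST is above ULN. Leave the symptom limb as it is.

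**Cost.** One limb and one clause. ALT, AST and bilirubin are already collected, so no test is added. The INR half works only where local results exist on Day 1 and on treatment.

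**Downside.** A few subjects whose bilirubin or INR rises from sepsis or biliary disease may be stopped permanently. The qualifier on expected rises limits this. Under it, a case like the PN004 subject, whose elevations the investigator thought could reflect septic shock or past gallstones, could still continue. The qualifier relies on investigator attribution, as limb 1 and the ECI note already do.
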